1.2 SCHEMA

1.3 SCHEDULE OF ACTIVITIES (SOA)

Table 1. Schedule of Activities

| | Screening (-6 weeks) | Baseline (Day 1 +/- 2 days) | Week 2 (Day 15+/- 7 days) | Week 6 (Day 43+/- 10 days) | Week 12 (Day 85 +/- 10 days) | Week 16 Follow- up (phone call) Day 113 +/- 10 days | Early Termination Visit | Week 28 Long-Term Follow-up (Month 3) +/- 2 weeks | Week 36 Long-Term Follow-up (Month 6) +/- 2 weeks | Week 60 Long-Term Follow-up (Month 12) +/- 2 weeks |
|--|-------------------------|--------------------------------------|------------------------------------|--|---|---|-------------------------------|---|---|--|
| Informed Consent and HIPAA Authorization | X | | | | | | | | | |
| Review Inclusion/Exclusion Criteria | X | X | | | | | | | | |
| Demographics & Medical History | X | | | | | | | | | |
| Physical Exam | | X | | | X | | X | X | X | X |
| Vital Signs ^A | X | X | X | X | X | | X | X | X | X |
| Standardized lifestyle counseling | | X | | | | | | | | |
| Height, weight, (calculated BMI) waist and hip measurements ^C | X | X | X | X | X | | X | X | X | X |
| Alcohol Use Disorders Identification Test (AUDIT) | X | | | | | | | | | |
| Dietary Assessment (Food Frequency Questionnaire) | | X | | | X | | X | | | |
| MRI | | X | | | X | | X | X | X | X |
| ECG | | X | X | | | | | | | |
| PROMIS Questionnaires (fatigue, depression, anxiety) | | X | | | X | | X | | | |
| Beverage Questionnaire | | X | | | X | | X | | | |
| Tanner Staging (self-administered) | X | | | | | | | | | |
| Physical Activity Assessment (Block) | | X | | | X | | X | | | |
| Local Urine Pregnancy Test (WOCBP) | | X | X | X | X | | X | X | X | X |
| Urinalysis (UA) | X | X | X | X | X | | X | X | X | X |
| Blood Draw ^B | X | X | X | X | X | | X | X | X | X |

| | | | | | | | | | | |
|----------------------------------|---|---|---|---|---|---|---|---|---|---|
| De novo lipogenesis (substudy) | | X | | | X | | | | | |
| Postprandial lipid (substudy) | | X | | | X | | | | | |
| Instructions for Drug Compliance | | X | X | X | | | | | | |
| Drug Dispense | | X | | X | | | | | | |
| Identify clinical follow-up plan | | | | | X | | X | | | |
| Adverse Events Review | | X | X | X | X | X | X | X | X | X |
| Concomitant Medication Review | X | X | X | X | X | X | X | X | X | X |
| Assess Drug Accountability | | | X | X | X | | X | | | |

A – Vital signs to include: temperature, pulse, respirations, and seated blood pressure

B – See details below in Table 2. Blood Draw Schedule

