C – Measurements taken in duplicate at each timepoint and a mean will be calculated and recorded

Table 2. Specimen Collection Schedule

| | Screening (-6 weeks) | Baseline (Day 1) | Week 2 (Day 15+/- 7 days) | Week 6 (Day 43+/- 10 days) | Week 12 (Day 85 +/- 10 days) | Early Term Visit | Week 28 Long-term Follow-up (Month 3) | Week 36 Long-term Follow-up (Month 6) | Week 60 Long-term Follow-up (Month 12) |
|--|-------------------------|---------------------|---------------------------------|----------------------------------|------------------------------------|------------------------|--|--|---|
| Local Labs: | | | | | | | | | |
| CMP ^A | X | X | X | X | X | X | X | X | X |
| Creatine phosphokinase (CPK) | X | X | X | X | X | X | X | X | X |
| CBC ^B | X | | | | X | X | X | X | X |
| GGT | X | X | | X | X | X | X | X | X |
| Clinical Lipid Profile ^C | X | | | | | | X | X | X |
| PT/INR | X | X | | X | X | X | X | X | X |
| HbA1c | X | X | | | X | X | X | X | X |
| Urinalysis | X | X | X | X | X | X | X | X | X |
| Central Labs: | | | | | | | | | |
| Plasma & Serum (storage) ^D | X | X | X | X | X | X | X | X | X |
| Urine (storage) ^D | X | X | X | X | X | X | | | |
| Buffy coat for DNA ^D | X | | | | | | | | |
| Fasting lipids ^{E, F} | | X | | X | X | X | | | |
| Fasting apolipoproteins ^{E, G} | | X | | X | X | X | | | |
| Fasting lipoprotein particle sizes ^H | | X | | X | X | X | | | |
| Inflammation (hsCRP) ^E | | X | | X | X | X | | | |
| Liver Function panel ^{E, I} | | X | | X | X | X | | | |
| Diabetes Panel ^{E, J} | | X | | X | X | X | | | |
| Pharmacokinetics | | | X | X | X | X | | | |
| Metabolomics ^D | | X | | | X | X | | | |

A – Comprehensive Metabolic Panel (CMP) includes: Alb, total bilirubin, Ca, CO₂, Cl, Creat, Glu, Alk, Phosphatase, K, TP, Na, ALT, AST, BUN (reflex to direct bilirubin if total bilirubin is elevated)

B – Complete Blood Count (CBC) includes: WBC, RBC, HGB, HCT, MCV, MCH, MCHC, RDW, PLT, neutrophils, lymphs, monocytes, eosinophils, basophils

C – Clinical Lipid Profile includes: cholesterol, triglyceride, HDL, LDL, VLDL

D – Processed locally, shipped to Emory University Biorepository

E – Analyzed by the Cardiovascular Research Lab at the Atlanta VA

F – Fasting lipids includes: TG, CHOL, HDLc, LDLc

G – Fasting apolipoprotein includes: apoA-I, apoB, apoC-II, apoC-III, apoE

H – Analyzed at LabCorp (Liposcience)

I – Liver Function panel includes: ALT, AST

J – Diabetes Panel includes: Glu, INS, NEFA

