8 STUDY ASSESSMENTS AND PROCEDURES

8.1 EFFICACY ASSESSMENTS

Study Procedures:

Central Lab Tests

The primary and secondary outcomes listed below will be batched and measured at a central lab. At each indicated study visit (see SOA), plasma will be collected, aliquotted and frozen within 2 hours of collection and shipped to the Cardiovascular Research Lab at the Atlanta VA. After all study visits are completed and samples are obtained for all participants, the following tests will be measured:

- Lipid panel (TG, CHOL, HDLc, LDLc)
- Apolipoprotein panel (apoA-1, apoB, apoC-II, apoC-III, apoE)
- hsCRP
- Liver function panel (AST, ALT)
- Diabetes panel (GLU, INS, NEFA)
- Pharmacokinetics (Week 2, Week 6, Week 12 and in sub-study participants at Emory 0, 2, 4 and 6 hour)

Local (safety) labs

In order to assure the safety of participants at the time of their participation in the study, the labs listed below will be performed locally at the time of the visits and reviewed by the study staff. For those labs that are measured by the local lab and by the central lab (ALT, AST, Glu, Lipids) the central lab measurements will be used for outcome analysis. In the case that a central lab is missing, this will be noted and if the local lab is available it will be used. (also see SOA).

- CMP (includes Glu, BUN, Creatinine, Lytes, Calcium, Total Protein, Albumin, Alk Phos, AST, ALT, Total Bilirubin)
- CBC (includes WBC, RBC, HGB, HCT, MCV, MCH, MCHC, RDW, PLT)
- GGT
- CPK
- Lipid profile (includes cholesterol, triglycerides, HDL, LDL, and VLDL)
- HbA1c
- UA (includes chemical analysis, blood, nitrites, leukocyte esterase, protein)
- PT/INR

Imaging:

Limited MRI (no contrast) of the abdomen to measure percent hepatic steatosis and the liver multiscan. The Resonance Health (HepaFat) scan will be used for liver fat and pancreatic fat and the Perspectum Liver Multiscan (LIF and cT1 scores) will be used for inflammation and fibrosis. Body composition will be assessed by AMRA Medical AB (AMRA).

Patient reported outcomes:

PROMIS questionnaires fatigue, anxiety and depression (see Appendix B)

Study Procedures by Visit:

Please refer to Section 1.3 Schedule of Activities for additional visit details

Unscheduled Visits:

- Repeat MRI or labs
- Rescreening Visit
- Repeat ALT (for screening)
- Early Termination Visit

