8.2 SAFETY AND OTHER ASSESSMENTS

Specific Safety Measures:

Hemoglobin decrease

For a hemoglobin decrease of > 1.5 g/dL from baseline during the study, repeat hematology studies and reflexive evaluation of reticulocyte count will be performed. The subject's past medical history, concomitant medications (including over the counter drugs and herbal supplements), and any recent symptoms (e.g., bleeding, shortness of breath, fatigue) will be reviewed to determine a potential etiology and make a clinical assessment of the significance of the finding.

Creatinine increase

If, at any visit, a creatinine increase of > 0.3 mg/dL (27 µmol/L) from baseline, a GFR decrease of >15 mL/min from baseline is observed, a repeat chemistry/urinalysis will be performed within seven days. The subject's past medical history, concomitant medications (including over the counter drugs and herbal supplements), and any recent symptoms (e.g., fatigue, malaise, polyuria/oliguria, or palpitations) will be reviewed to determine a potential etiology and make a clinical assessment of the significance of the finding.

Possible muscle and liver injury

For muscle injury, CPK, hepatic, and renal function laboratory data will be integrated with myopathy signs and symptoms.

For liver injury, laboratory data will be integrated with hepatic signs and symptoms. Alanine aminotransferase increases > 2 × baseline with symptoms of hepatitis or > 3 × baseline with or without symptoms of hepatitis will be evaluated and managed according to guidelines for studies in patients with pre-existing liver disease. This includes a repeat assessment as soon as possible to confirm the findings and a clinical evaluation. If the participant has signs or symptoms of hepatitis or ALT > 5x baseline, the study drug will be temporarily discontinued.

Data to be provided to the participants – At a minimum, the locally run clinical labs and MRI liver fat result from baseline will be provided to each patient at the end of the study and reviewed with them by a study investigator. This includes the CMP, CBC, GGT, hemoglobin A1c, insulin, glucose and fasting lipids. The investigator may choose to share other locally run clinical labs from other time points with the participant.

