10.1.2 STUDY DISCONTINUATION AND CLOSURE

This study may be temporarily suspended or prematurely terminated if there is sufficient reasonable cause. The DSMB will review all AEs and SAEs and may suspend or terminate the study for safety concerns. AEs will be reviewed quarterly and for any SAE, an ad hoc meeting of the DSMB will be convened within 10 business days to review the event.

Written notification, documenting the reason for study suspension or termination, will be provided by the suspending or terminating party to study participants, investigators, Gemphire, the Investigational New Drug (IND) sponsor and regulatory authorities. If the study is prematurely terminated or suspended, the Principal Investigator (PI) will promptly inform study participants, the Institutional Review Board (IRB), and sponsor and will provide the reason(s) for the termination or suspension. Study participants will be contacted, as applicable, and be informed of changes to study visit schedule.

Circumstances that may warrant termination or suspension include, but are not limited to:

- Determination of unexpected, significant, or unacceptable risk to participants
- Demonstration of efficacy that would warrant stopping
- Insufficient compliance to protocol requirements
- Data that are not sufficiently complete and/or evaluable
- Determination that the primary endpoint has been met
- Determination of futility

Study may resume once concerns about safety, protocol compliance, and data quality are addressed, and satisfy the sponsor, IRB and/or Food and Drug Administration (FDA).

Patient-specific trial stopping rules include:

- In any patient who develops an AE of grade 3 that is probably or possibly related to study drug and any patient who develops a grade 4 or higher CTCAE regardless of causality assessment, investigational product will be discontinued.
- Hemoglobin will be assessed by central laboratory evaluation. For a hemoglobin decrease of > 1.5 g/dL from baseline during the study, repeat hematology studies and reflexive evaluation of reticulocyte count will be performed. The patient's past medical history, concomitant medications (including over the counter drugs and herbal supplements), and any recent symptoms (e.g., bleeding, shortness of breath, fatigue) will be reviewed to determine a potential etiology and make a clinical assessment of the significance of the finding.

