- If hemoglobin falls >3.0 g/dL without any clear cause, then the investigator should discontinue the investigational product and hemoglobin should be monitored until it returns to a level of no less than 1.0 g/dL below baseline. At this time, the investigator can consider restarting the investigational product and recheck hemoglobin levels one and two weeks after re-initiation of investigational product. If hemoglobin levels decrease >3 g/dL again, investigational product should be discontinued and the subject should continue with all other study procedures. Hemoglobin should continue to be monitored until it returns to a level of no less than 1.0 g/dL below baseline.
- If, at any visit, a creatinine increase of > 0.3 mg/dL (27 μ mol/L) from baseline, a GFR decrease of > 15 mL/min from baseline, or a > 30 urinary albumin:creatinine ratio mg/g is observed, a repeat chemistry/urinalysis will be performed within one week. The patient's past medical history, concomitant medications (including over the counter drugs and herbal supplements), and any recent symptoms (e.g., fatigue, malaise, polyuria/oliguria, or palpitations) will be reviewed to determine a potential etiology and make a clinical assessment of the significance of the finding.
- Patients with persistent serum creatinine changes of > 0.3 to < 0.5 mg/dL will be evaluated by the investigator to determine if the subject has any signs and symptoms of renal injury. If the investigator determines that the biomarkers along with the signs and symptoms are consistent with renal injury, then investigational product should be discontinued, and the subject should continue with all future protocol assessments.
- If at any time there is a doubling of serum creatinine or a decrease > 50% in GFR from baseline, then investigational product should be discontinued immediately. The patient will be followed until renal parameters return to baseline or normal levels. The investigator can determine based on signs, symptoms and laboratory data whether or not to reinitiate investigational product and continue with scheduled monitoring. Regardless of whether or not investigational product is reinitiated subjects should continue with all future protocol assessments.

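### The hemoglobin stop/restart rule has no scheduled hemoglobin between the first dose and the end-of-treatment visit; add a local CBC at Day 1, Week 2 and Week 6.

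*Combined protocol and SAP*

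**What the plan says.** Section 10.1.2 has a tiered hemoglobin rule. A fall of more than 1.5 g/dL from baseline leads to repeat hematology and a reticulocyte count; Section 8.2 has the same trigger ("For a hemoglobin decrease of > 1.5 g/dL from baseline during the study, repeat hematology studies"). The next tier is a stop: "If hemoglobin falls >3.0 g/dL without any clear cause, then the investigator should discontinue the investigational product". Once hemoglobin is back within 1.0 g/dL of baseline, the drug may be restarted, and the investigator is to "recheck hemoglobin levels one and two weeks after re-initiation of investigational product". On who measures it, Section 10.1.2 says: "Hemoglobin will be assessed by central laboratory evaluation".

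Table 2 (Section 1.3) lists hemoglobin only within the CBC, which is a local test. The CBC is marked at Screening, Week 12, Early Termination and the three long-term follow-up visits. It is blank at Baseline, Week 2 and Week 6, and Table 3 shows no CBC volume at those three visits.

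The chemistry panel that feeds the creatinine rule is marked at every visit: "CMP ^A | X | X | X | X | X | X | X | X | X". Table 1 has blood drawn at every clinic visit from Screening to Week 12: "Blood Draw ^B | X | X | X | X | X".

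On timing, Section 8.1 says of the central tests: "After all study visits are completed and samples are obtained for all participants, the following tests will be measured". Of the local safety tests it says: "the labs listed below will be performed locally at the time of the visits and reviewed by the study staff". The central list has no hematology.

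**The concern.** A stop-and-restart rule assumes that a fall is found while there is still treatment to stop and resume. Here the first scheduled hemoglobin after dosing comes at Day 85. Drug is dispensed only at Baseline and Week 6 (Section 6.2.1), so the Week 6 supply is handed out with no hemoglobin since before the first dose, and nothing is dispensed after the Week 12 result. No scheduled result leads to the restart clause.

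The reference value is also weak. With no Day 1 CBC, the only scheduled pre-dose hemoglobin is the Screening value, taken before the 4-6 week lead-in.

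The protocol itself treats this as a real risk. Section 2.3.1 includes hemoglobin decrease among the risks it singles out as important. Section 2.2 reports falls at every dose level (30-300 mg/kg/day) in the 26-week rat study, and mild, partly reversible red-cell changes at all doses in monkeys. The drug has not been tested in children before, and Section 2.3.1 says juvenile toxicity studies are unfinished. Hematology is a listed safety endpoint in Section 3, yet a completing child contributes one scheduled value from the treatment period.

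**Working it through.** **Are the blanks real?** Table 3 can be rebuilt from its rows. The safety-lab subtotal is CMP + CBC + PT/INR + HbA1c.
- Baseline: 8.5 + 0 + 2.7 + 4 = 15.2 mL (printed 15.2). With a CBC it would be 19.2.
- Week 2: 8.5 mL (printed 8.5). With a CBC it would be 12.5.
- Week 6: 8.5 + 0 + 2.7 + 0 = 11.2 mL (printed 11.2). With a CBC it would be 15.2.
- Safety total 130.9 + central total 75 = 205.9 mL, as printed.

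The printed totals reproduce only if no CBC is drawn at these visits, so the blanks are not a table-reading fault.

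**Counts, Screening to Week 12.** Creatinine (CMP): 5 of 5 visits. Hemoglobin (CBC): 2 of 5. Scheduled hemoglobin values after the first dose and before Week 12: 0 now, 2 with the fix.

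**Longest wait from a fall to the next scheduled value.** Visits are on Days 1, 15, 43 and 85.
- Now: 85 - 1 = 84 days. With the Week 12 window (Day 95): 94.
- With Weeks 2 and 6 added: the longest gap is 85 - 43 = 42 days. With windows (Day 33 to Day 95): 62.

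**Mean wait.** Assume a fall is equally likely on any of the 84 treatment days and is visible at once. The documents give no time course, so this is an assumption. Mean wait = sum of squared gaps / (2 × 84).
- Now: 84² / 168 = 42.0 days.
- Weeks 2 and 6: (14² + 28² + 42²) / 168 = 2744 / 168 = 16.3 days.
- Week 6 only: (42² + 42²) / 168 = 21.0 days.
- Week 2 only: (14² + 70²) / 168 = 30.3 days.

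**By time of fall**, taking the middle of each interval (Days 8, 29 and 64):
- Before Week 2: 77 days now, 7 with the fix.
- Week 2 to Week 6: 56 days now, 14 with the fix.
- After Week 6: 21 days now, 21 with the fix (no gain).

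**Dosing days spared by a stop.** Week 2: 85 - 15 = 70. Week 6: 85 - 43 = 42. Now, from a scheduled value: 0. These are upper limits, because the rule needs the absence of a clear cause and allows a restart.

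**Age of the reference value at Week 12.** Lead-in of 28-42 days (Section 4.2) + 84 = 112-126 days now; 84 days with a Day 1 CBC.

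**False alarms.** Assume a within-child SD of 0.4 to 0.6 g/dL, which is not in the documents. The SD of a difference is SD × √2. There are 40 × 2 = 80 added on-treatment values.
- Chance fall above 1.5 g/dL: 0.40% (SD 0.4) to 3.85% (SD 0.6); × 80 gives about 0.3 to 3.1 work-ups in the whole trial.
- Chance fall above 3.0 g/dL at SD 0.6: 0.020% × 80 = 0.016 stops.

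**The case against.** The strongest counter-argument is regulatory history. The amendment log for Version 1.1 attributes both the Week 12 CBC and the patient-specific stopping rules to FDA requests, so sparse CBC sampling may not be a simple oversight. The log does not show, however, that mid-treatment CBCs were considered and rejected.

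Second, the rule is not wholly idle. Section 8.1 allows unscheduled repeat labs, adverse events are reviewed at Weeks 2 and 6, and the Week 12 CBC can still start a work-up and follow-up. This stands, and it narrows the gap to falls without symptoms during dosing. Those are the falls a scheduled test is meant to catch.

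Third, the human data are reassuring: 901 people exposed, up to twelve weeks at doses as high as 900 mg, with only small hemoglobin decreases that were also seen with placebo. This stands as a limit on the urgency. It does not explain a stop rule that has no data to act on.

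Fourth, Week 6 alone gives most of the gain in mean wait: 21.0 of 25.7 days (82%), with Week 2 adding 4.7. That is correct under the equal-likelihood assumption, and it supports Week 6 as the fallback if only one CBC is acceptable.

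Last, eosinophilia above 5% in Section 8.3.10 also needs a CBC differential, but it is one item in a symptom list within a liver-injury plan and does not imply routine screening. It is a side benefit and does not carry the point.

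**Conclusion.** The concern holds. Between the first dose and the end-of-treatment visit the plan has no scheduled hemoglobin, so the stop and restart steps cannot be set off by a scheduled result. The central laboratory cannot fill the gap: none of its listed tests includes hemoglobin, and its assays are batched after the last participant's last visit.

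The count of values and the longest waits (84 days now, 42 with the fix) come directly from the visit schedule and need no assumption. The mean waits depend on equal likelihood of a fall over the treatment period, and the false-alarm range depends on the assumed SD. Neither assumption is needed for the conclusion. This is a change that should be made, given its low cost; the adult safety record argues against rating it higher.

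**What to change.** In Table 2, add a local CBC with differential at Baseline (Day 1, before the first dose), Week 2 and Week 6, and add 4 mL at each in Table 3. Act on the results under the existing rules in Sections 8.2, 8.3.10 and 10.1.2, with thresholds unchanged. In Section 10.1.2, name the local CBC in place of the central laboratory. The clinical team should state which pre-dose value counts as baseline; a Day 1 value would now exist. If only one on-treatment CBC is acceptable, choose Week 6.

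Cost:
- No new visits or needle sticks.
- 3 × 4 = 12 mL more per child: 205.9 to 217.9 mL, or 12 / 205.9 = 5.8%. Baseline goes from 29.2 to 33.2 mL, Week 2 from 15.5 to 19.5 and Week 6 from 28.2 to 32.2. Sub-study Baseline goes from 85.2 to 89.2 mL.
- 40 × 3 = 120 local CBCs, and the few chance work-ups estimated above.
- A protocol amendment with IRB approval and, since this is a safety rule under an IND, notice to FDA.

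When Table 3 is reissued, its total with sub-study should be corrected too: it prints 327.5 mL, but its parts give 205.9 + 9 + 112 = 326.9 mL, or 338.9 mL after this change.

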7 STUDY INTERVENTION DISCONTINUATION AND PARTICIPANT DISCONTINUATION/WITHDRAWAL

7.1 DISCONTINUATION OF STUDY INTERVENTION

Discontinuation from gemcabene does not mean discontinuation from the study, and remaining study procedures should be completed as indicated by the study protocol. If a clinically significant finding is identified (including, but not limited to changes from baseline) after enrollment, the investigator or qualified designee will determine if any change in participant management is needed. Any new clinically relevant finding will be reported as an adverse event (AE).

The data to be collected at the time of study intervention discontinuation (Early Termination Visit) will include the following:

- Blood tests
- MRI
- Vital signs, physical measurements, and a physical examination
- Questionnaires (Food Frequency Questionnaire, PROMIS Questionnaires, Beverage Questionnaire, Physical Activity Assessment)
- Urine collection and pregnancy test (in WOCBP)
- Adverse event and concomitant medication review

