7.2 PARTICIPANT DISCONTINUATION/WITHDRAWAL FROM THE STUDY

Participants are free to withdraw from participation in the study at any time upon request.

An investigator may discontinue or withdraw a participant from the study for the following reasons:

- Pregnancy
- Significant study intervention non-compliance
- If any clinical adverse event (AE), laboratory abnormality, or other medical condition or situation occurs such that continued participation in the study would not be in the best interest of the participant
- Disease progression which requires discontinuation of the study intervention

- If the participant meets an exclusion criterion (either newly developed or not previously recognized) that precludes further study participation
- Participant unable to receive gemcabene for ≥ 14 days.

The reason for participant discontinuation or withdrawal from the study will be recorded on the Case Report Form (CRF). Subjects who sign the informed consent form but do not receive the study intervention may be replaced. Subjects who sign the informed consent form, receive the study intervention for > 4 weeks, and subsequently withdraw, or are withdrawn or discontinued from the study, will not be replaced.

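### The renal drug-stop rules in 10.1.2 leave a gap: a creatinine rise of 0.5 mg/dL or more that stops short of doubling meets neither rule

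*Combined protocol and SAP*

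**What the plan says.** The patient-specific stopping rules in 10.1.2 contain three renal steps.

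- **Retest rule.** A rise above 0.3 mg/dL, a GFR fall above 15 mL/min, or a urinary albumin:creatinine ratio above 30 mg/g leads to repeat testing within a week and a clinical assessment. It has no upper limit and names no drug action. Section 8.2 repeats it without the albumin:creatinine ratio.
- **Rule A.** "Patients with persistent serum creatinine changes of > 0.3 to < 0.5 mg/dL will be evaluated by the investigator". The drug action follows: "If the investigator determines that the biomarkers along with the signs and symptoms are consistent with renal injury, then investigational product should be discontinued".
- **Rule B.** "If at any time there is a doubling of serum creatinine or a decrease > 50% in GFR from baseline", the drug is stopped at once.

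Three general provisions also bear on the drug decision.

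- The first stopping rule in 10.1.2 is mandatory and goes by adverse event grade. It covers a grade 3 event judged at least possibly drug-related and, whatever the cause, every event of grade 4 or above: "any patient who develops a grade 4 or higher CTCAE regardless of causality assessment, investigational product will be discontinued".
- Under 7.1, after a clinically significant finding, "the investigator or qualified designee will determine if any change in participant management is needed". If the drug is stopped, "remaining study procedures should be completed as indicated by the study protocol".
- Section 7.2 is permissive: "An investigator may discontinue or withdraw a participant from the study for the following reasons". The reasons include a laboratory abnormality and a newly met exclusion criterion. Exclusion criterion 4 is an eGFR below 60.

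**The concern.** Rule A has a ceiling of 0.5 mg/dL and Rule B starts at doubling. Unless doubling happens to fall at or below a 0.5 mg/dL rise, the two do not meet. The explicit instruction to stop the drug when renal injury is judged present then applies to the smaller persistent rise and not to the larger one.

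This matters because 2.3.1 lists creatinine increase among the drug's important potential risks and says that juvenile toxicity studies are unfinished. Section 2.2 gives the kidney as the main route of elimination, and 4.2 describes this as the first study in children. For the larger rise, each investigator would have to reach a drug decision from general wording.

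A smaller point in the same section: the retest rule relies on an albumin:creatinine ratio that is not listed as a measurement in Tables 1 to 3 or in 8.1.

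**Working it through.** The plan gives no figure of its own to reproduce here. The check maps the rules onto creatinine values.

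**Inputs.** From 10.1.2: Rule A covers a rise *r* with 0.3 < *r* < 0.5 mg/dL; Rule B covers creatinine of at least twice baseline, or a GFR fall above 50%. From 5.2: GFR is by the bedside Schwartz calculator. That is stated for eligibility; I assume it is also used on study, and that at fixed height eGFR is inversely proportional to creatinine. Baseline creatinine *b* is not given, so 0.6, 0.8 and 1.0 mg/dL are assumed values.

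**Step 1: where the rules leave a gap.** Doubling means *r* = *b*. Neither rule applies when 0.5 ≤ *r* < *b*. The width is 2*b* − (*b* + 0.5) = *b* − 0.5, which is positive only if *b* > 0.5 mg/dL. At *b* ≤ 0.5 there is no gap.

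**Step 2: does the GFR limb of Rule B close it?** The fractional eGFR loss is 1 − *b*/(*b* + *r*) = *r*/(*b* + *r*). This reaches 50% only when *r* = *b*, that is, at doubling. The GFR limb adds nothing inside the gap.

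**Step 3: size of the gap.** The loss at its lower edge is 0.5/(*b* + 0.5) and at its upper edge 50%. Rule A runs from 0.3/(*b* + 0.3) to 0.5/(*b* + 0.5).

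| Assumed baseline (mg/dL) | Creatinine in the gap (mg/dL) | Width | eGFR loss in the gap | eGFR loss under Rule A |
|---|---|---|---|---|
| 0.6 | 1.1 to <1.2 | 0.1 | 45.5% to <50% | 33.3% to 45.5% |
| 0.8 | 1.3 to <1.6 | 0.3 | 38.5% to <50% | 27.3% to 38.5% |
| 1.0 | 1.5 to <2.0 | 0.5 | 33.3% to <50% | 23.1% to 33.3% |

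Example at *b* = 0.8: a persistent rise of 0.4 is a loss of 0.4/1.2 = 33.3% and has an explicit stop-if-injury rule. A rise of 0.6 is a loss of 0.6/1.4 = 42.9% and has none.

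**Step 4: do the other provisions supply the missing instruction?**

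- The retest rule and 8.2 cover the gap for testing and assessment, but name no drug action.
- Section 7.1 requires a management decision after a clinically significant finding, with no renal criterion.
- Section 7.2 allows withdrawal but does not require it.
- The grade-based stop is mandatory, but the documents tie no creatinine value to a grade, so how far it reaches into the gap cannot be shown.

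**Step 5: dosing time that could remain.** Section 2.3.1 says past increases appeared in the first 2 to 4 weeks, so they would be seen at Week 2 (Day 15) or Week 6 (Day 43). With Week 12 at Day 85 there are 84 dosing days.

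- After Week 2: 85 − 15 = 70 days (83%). Allowing for visit windows, 75 − 22 = 53 to 95 − 8 = 87.
- After Week 6: 85 − 43 = 42 days (50%). Allowing for visit windows, 75 − 53 = 22 to 95 − 33 = 62.
- After a further 7 days for the repeat test, nominally 63 and 35 days.

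These are ceilings. They assume that nobody stops the drug under the general provisions.

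**The case against.** The strongest reply is that little is really missing. Evaluation has no ceiling, since every rise above 0.3 mg/dL is retested and assessed, and 7.1 then compels a management decision if the finding is significant. Rule A is itself a matter of judgement, and a sensible investigator would treat a larger rise at least as strictly. Nothing tells anyone to continue dosing, and the list of stopping rules is not presented as exhaustive.

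Section 7.2 also reaches well into the gap. eGFR is already below 60 at the gap's lower edge if baseline eGFR is below 60 × (*b* + 0.5)/*b*: 90, 97.5 and 110 at baseline creatinine 1.0, 0.8 and 0.6. At the upper edge the limit approaches 120. Past increases were minor and transient according to 2.3.1, and 2.2 attributes them to haemodynamics, so cases may be rare. The timing in 2.3.1 comes from those minor increases, so applying it to larger rises is extrapolation. The albumin:creatinine ratio is one of three alternative prompts, and the other two work without it.

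Most of this stands, and it limits the consequence: a child in the gap is neither unmonitored nor without a route to stopping. It does not restore the missing sentence. Section 7.2 is optional and concerns leaving the study, whereas the renal rules stop the drug and keep the child under assessment. A written rule should not be less explicit for the larger rise and rely on the investigator to reverse that.

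**Conclusion.** The concern holds, in a limited form. The explicit renal stop clause ends at 0.5 mg/dL and does not run up to the immediate-stop rule, so for any baseline above 0.5 mg/dL a band of larger rises has no renal drug-stop instruction. At assumed baselines of 0.6 to 1.0 mg/dL the band is 0.1 to 0.5 mg/dL wide and starts at eGFR losses of 45.5% down to 33.3%. The result rests on the assumed baselines and on eGFR being inversely proportional to creatinine.

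The number of children who would fall in the band cannot be estimated from the documents and may be small. Power and the primary analysis are not affected. It should still be corrected, because it is a wrong limit in a safety rule for a named risk in a first paediatric study. The unscheduled albumin:creatinine ratio is secondary.

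**What to change.** In 10.1.2, change the range in Rule A to a persistent rise of more than 0.3 mg/dL and less than doubling from baseline, and keep the rest of the rule. The gap is then empty at every baseline. Any stricter action at 0.5 mg/dL and above can be left to the sponsor and the DSMB, which includes paediatric nephrology. Section 8.2 needs no change.

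For the albumin:creatinine ratio, either run it on the urine already collected and list it in the schedule, or delete the prompt.

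The cost is one phrase in a protocol amendment, which needs IRB approval before it takes effect, plus one added assay if the ratio is kept. No extra visits or patients are needed.
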